	
 • Salivary function and subjective dry mouth, determined by mean overall and individual salivary amounts, compositional analysis, and QoL xerostomia survey scores at 1, 3, 6, 12, and 24 months. • Shear wave velocity with acoustic radiation force impulse, measured by ultrasound (US) of submandibular glands at 3, 6, and 12 months • Feasibility for a future Phase 1 dose-escalation study will be based on drop-out rate.
Study Design	This is a single-center pilot study designed to determine the safety and tolerability of autologous bone marrow-derived MSCs in patients with xerostomia after undergoing radiation therapy for HNC.
IND Number	23026
Study Intervention	
Adults with xerostomia after radiation therapy for HNC will undergo one-time injection of $10 (8 - 12) \times 10^6$ MSCs into one submandibular gland.
 
A second injection of $10 (8 - 12) \times 10^6$ MSCs will be offered for injection into each subject's contralateral submandibular gland as no DLT's were noted in any of the study participants (sub study).

Total Number of Subjects	A total of 6-12 subjects will be enrolled from 1 study site.
Study Population	Male and females aged 18 to 90 years with xerostomia 2 years after undergoing radiation therapy for HNC.
Statistical Methodology	The pilot trial with 12 patients total enrolled will allow us to estimate 95% CI of adverse events (e.g. 1 of 6 patients results in a 95% CI of 0-64%). All patients will be analyzed for adverse events.
Estimated Subject Duration	The duration of the study for each subject is approximately 24 months.
Estimated Enrollment Period & Study Duration	Study enrollment and follow-up will occur over 6 months with the total expected duration of the trial to be 30 months.

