5.5 Rationale for Injection of Second Submandibular Gland

We have achieved our primary objective of evaluating the safety and tolerability of injection of interferon gamma stimulated MSCs into the submandibular gland. No patients have had a DLT within one month of injection. Indeed, only 3 patients reported pain (pain scale rating 1/10) with all 3 patients having resolution of their pain within 4 days. There were no serious adverse events. Now that the safety of this dose level of MSCs has been shown, injection of the contralateral submandibular gland at the same dose level will be undertaken. We are opening a phase I clinical trial in 2023 in which patients undergo bilateral submandibular gland injection with interferon gamma stimulated MSCs. In order to provide the most benefit for patients, bilateral injection is recommended, as this will allow for the regeneration of both submandibular glands, which provide the majority of unstimulated saliva.

Additionally, the UW PACT has demonstrated stability of the cryopreserved MSC IMP after storage (see Appendix 19.4 for stability data). Each patient's MSC IMP was cryopreserved, thawed, culture-rescued, and formulated for injection in the already conducted pilot clinical study. The MSC IMP utilized for the second injection is composed of MSCs that were manufactured and cryopreserved at the same time as the MSCs for the first injection.

Each patient has cryopreserved autologous MSCs sufficient to allow for injection of the contralateral submandibular gland at dose level 0. We will utilize the cryopreserved MSCs for the contralateral gland injection, removing the need for another bone marrow aspiration and culturing of cells. The MSC IMP for the second injection will be identical to the first injection with the exception that these MSCs have been in cryopreservation longer.

6.0 THIS AMENDMENT WILL BE FORWARDED TO THE FDA FOR REVIEW PRIOR TO IMPLEMENTATION. STUDY OBJECTIVES AND ENDPOINTS

Objectives	Endpoints
Primary To evaluate the safety and tolerability of MSCs for subjects with xerostomia after radiation for HNC.	Recommended starting dose of MSCs for a Phase I dose-escalation study, determined by the proportion of subjects experiencing dose-limiting toxicity (DLT), where DLT is defined as: submandibular pain > 5 on a standard 10-point pain scale of 0-10 at 1-month after MSC injection OR any serious AE OR any of the selected toxicities listed in section 9.7 within one-month post-injection.
Secondary	

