7.0 STUDY DESIGN

7.1 General Design

This single-center, open-label, non-randomized, non-placebo controlled, single-group assignment, pilot study is designed to determine the safety and tolerability of autologous bone marrow-derived MSCs in patients with xerostomia after undergoing radiation therapy for HNC. A total of 6- subjects will be enrolled at UW-Madison for unilateral gland injection (dose level 0). Subject accrual will occur over 0.5 years with the total duration of the trial expected to be approximately 2.5 years.

Following the completion of screening/baseline procedures, and written consent, eligible subjects will undergo bone marrow aspirate in order to obtain MSCs. MSCs will be prepared as described in Section 9.2.

The MSC IMP (dose level 0) will be injected into one submandibular gland under local anesthesia, in the gland that received the lowest radiation dose. Patients with only one submandibular gland will be ineligible. All subjects will be called by a study coordinator 3 days (+/- 2 days) after injection to assess pain and will have a phone visit with a physician 1 week (+/- 2 days) after injection during which the investigator will assess pain and ask about the area of injection regarding redness and/or swelling. All subjects will complete a pain diary with daily entries over the first month to record the occurrence and severity of pain using a 0-10 visual analog scale and occurrence and severity of other adverse events (e.g., redness, swelling, warmth, tenderness, rash, pruritis, nausea, vomiting, fatigue). Patients will also keep a log of all pain medications taken including both narcotic and non-narcotic medications (e.g. ibuprofen, acetaminophen, etc.) for the first month. Subjects will complete 5 follow-up visits over the course of 24 months – at 1, 3, 6, 12, and 24 months following the intervention. Salivary collection for analysis as well as QoL surveys will be obtained at these visits.

Additional Gland Injection: The 6 subjects will be offered optional contralateral submandibular gland MSC injection at dose level 0 upon completion. The primary objective (1 month of follow-up after injection of MSCs) without any DLTs has now occurred.

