Subjects will also be offered injection of MSCs into the contralateral submandibular gland upon completion of the trial's primary objective (1 month of follow-up after injection of MSCs without any DLTs). The MSC IMP (dose level 0, from previously obtained bone marrow aspirate and culture) will be injected into the contralateral submandibular gland under local anesthesia. Secondary objectives will remain unchanged. Each subject will undergo salivary collection and completion of QoL forms just prior to second injection of MSC IMP. All subjects will complete follow up timepoints per the main study at 12 months (+/- 3 months) post second injection to analyze the benefit of the second injection by assessing secondary objectives including salivary amount and salivary QoL. This 12 month timepoint will allow for assessment of durable improvement, while not prolonging the overall study duration. Additionally, subjects will be monitored for AEs post-injection. All subjects will be called by a

study coordinator or physician 3 days (+/- 2 days) and 7 days (+/- 2 days) after injection to assess pain, redness, or other AEs. Subjects will also be seen 30 days (+/- 10 days), 90 days (+/- 14 days), 6 months (+/- 28 days), 12 months (+/- 3 months) and 24 months (+/- 3 months) after second MSC injection for safety evaluation and blood collection to assess for AEs.

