7.2 End of Study Definition

A subject is considered to have completed the study if they have completed all visits described in the study including the last visit listed in Section 10.1: Study Calendar.

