9.7 Dose-Reduction Schedule

The cohort of 6 participants will have staggered enrollment. A minimum interval of 14 days will occur between MSC injection of a subject and MSC injection in the subsequent subject, during which time there must be no SAEs and no AEs ≥ grade 3 that are probably or definitely attributable to MSC injection. The decision to proceed with enrollment of a subsequent subject within a dose cohort will be made by the PI based on the criteria stated above.

For purposes of possible dose reduction from Dose 0 to Dose -1, dose limiting toxicity is defined as a submandibular pain score > 5 (on a standard 0-10 pain scale) at one-month post-injection OR any serious AE probably or definitely caused by study treatment at any time within one-month post-injection OR any of the toxicities below within 1 month of injection:

- Grade 4 neutropenia > 5 days
- Grade 4 thrombocytopenia, or grade 3 thrombocytopenia with hemorrhage
- Grade 3-4 non-hematological toxicity **except**:
 - Grade 3 nausea, vomiting, and diarrhea lasting < 72 hrs in the absence of maximal medical therapy
 - Grade 4 vomiting and diarrhea lasting < 72 hrs in the absence of maximal medical therapy
 - Grade 3 fatigue < 5 days
 - Grade 3 hypertension in the absence of maximal medical therapy

- Grade 3 rash < 5 days is included as an exception
- Grade 3 metabolic abnormalities such as hypokalemia, hypomagnesemia, hypocalcemia, and hypophosphatemia should only be excepted from the DLT definition if they recover to Grade 1 or less within 48 hours.
- Grade 3 fatigue that persists < 7 days.
- Grade 3 rash that resolves to ≤ Grade 1 within 3 weeks.
- Grade 3 or 4 elevation in serum amylase and/or lipase that are not associated with clinical or radiographic evidence of pancreatitis.
- ≥ Grade 3 electrolyte abnormality that lasts < 72 hours, is not clinically complicated, and resolves spontaneously or responds to conventional medical intervention.
- Grade 3 nausea or vomiting that lasts < 48 hours, and resolves to ≤ Grade 1 either spontaneously or with conventional medical intervention.
- Grade 3 immune related AE (irAE) that resolves to ≤ Grade 1 or to baseline with immunosuppressive therapy within 3 weeks.

Additionally, patient enrollment and treatment will be temporarily halted if any of the following occur, pending review by the UWCCC DSMC and FDA if:

- Any death, irrespective of attribution by the investigator within 30 days of MSC injection
- Any (CTCAE v. 5) of grade 4 or higher

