13.8 Analyses of the Secondary Endpoints

Analyses of the secondary endpoints focus on efficacy of the IMP in the treatment of xerostomia and hyposalivation. All inferential analyses for the secondary outcome variables will be interpreted in the exploratory sense, only.

Patient-reported outcome measures will be evaluated by comparing the changes in salivary QOL from baseline to each follow-up visit and by assessing changes over time, within-group comparisons will be performed with the Wilcoxon signed-rank test.

Salivary flow rate analysis will be analyzed in a manner described by Gronhoj et al. 2018²⁴: by comparing the changes from baseline to each follow-up visit and changes over time, within-group comparisons will be performed with the Wilcoxon signed-rank test.

Salivary composition analyses will focus on qualitative aspects of saliva previously found to change following radiation treatment: salivary pH^{39,40}, total protein concentration (mg/mL)^{41,42}, amylase (mU/mL)^{39,43}, and mucins (MUC5B, mU/mL)^{43,44}. Given that MSCs will be injected into one of the submandibular glands which contain both serous and mucous acinar secretory cells, we will measure products of both types of cells (both= total protein and pH; serous= amylase; mucous= mucins). Salivary pH will be measured using a pH meter (Orion 9810BN, Thermo Scientific). Enzyme-linked immunosorbent assays (ELISAs) will be used to quantify total protein, amylase, and mucin levels. Saliva composition will be assessed on whole saliva samples collected from subjects at the screening visit and the in-person follow-up visits.

To assess the imaging characteristics of submandibular gland after MSC injection, salivary gland size will be measured by ultrasound⁴⁵. Ultrasound imaging is a non-ionizing, noninvasive imaging modality that can be quickly obtained in a standard exam room. Three-dimensional (3D) Bmode data sets will be acquired for tumor volume measurements. If post-RT submandibular glands suppress ultrasound waves to prevent the visualization of the lower outline of the gland, a 2D estimate of gland size will be made.

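### Section 13 was not adapted to the optional second injection: late saliva and QoL results pool one-gland and two-gland values, and the assessment taken just before the second injection is used in no analysis

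*Combined protocol and SAP*

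**What the plan says.** **The second injection.** Section 7.1 states: "The 6 subjects will be offered optional contralateral submandibular gland MSC injection at dose level 0 upon completion". It follows completion of the 1-month objective without DLTs. Section 5.5 reports that this objective has been met, and the text after it adds: "THIS AMENDMENT WILL BE FORWARDED TO THE FDA FOR REVIEW PRIOR TO IMPLEMENTATION". Section 7.1 gives the purpose of the later follow-up, with 12 months (± 3 months) after the second injection as the timepoint: "to analyze the benefit of the second injection by assessing secondary objectives including salivary amount and salivary QoL". It also provides a starting value: "Each subject will undergo salivary collection and completion of QoL forms just prior to second injection of MSC IMP". The sub-study calendar in 10.1 schedules saliva and QoL at the second injection and at 30 days, 90 days, 6 months and 12 months after it.

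**The analysis.** For saliva flow, 13.8 proceeds "by comparing the changes from baseline to each follow-up visit and changes over time, within-group comparisons will be performed with the Wilcoxon signed-rank test", and it treats patient-reported outcomes the same way. Section 13.2 separately describes one-way ANOVA with Tukey comparisons between baseline and post-injection timepoints. The design in Section 13 is the one-injection design: unilateral injection in 13.2, a one-time injection in 13.5, cells into one of the glands in 13.8. Section 13.3 adds an efficacy evaluation by dose received, without saying how one injection is told apart from two. Section 13.1 places the main analysis after the 24-month visit, without saying which injection that visit is counted from.

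**The concern.** The amendment changed what subjects may receive but not how their data are analysed. Sialometry (11.3) and composition (11.4) use whole saliva, and the QoL instruments are completed by the patient as a whole. None of these outcomes can show which gland produced a change.

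Two things follow if Section 13 is applied as written.

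- A main-study visit after a subject's second injection is one more follow-up visit compared with the original baseline. It goes into the same summary as visits from subjects with one treated gland. A late result could then reflect one injection, two, or a mixture, and the table would not show which.
- The second injection has a stated purpose and its own starting value, but no stated comparison. If its benefit is read from 13.8 with the original baseline, a lasting gain from the first injection is counted as benefit of the second.

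**Working it through.** The plan gives no figure on this point. The check sets the sections side by side and then uses simple arithmetic.

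**1. Which visits can be affected.** On the main calendar (10.1), saliva and QoL after the first injection fall at 1, 3, 6, 12 and 24 months: 5 assessments. The sub-study adds one just before the second injection and four after it (30 days, 90 days, 6 and 12 months): 5 more. A re-injected subject who keeps both schedules can have up to 5 + 5 = 10 assessments after the first injection, against the five timepoints in the endpoint (Section 6.0). Section 13 does not say where the additional five belong.

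**2. Size of the pooling.** Let u of the 6 subjects be re-injected before a given main visit, with all six attending. The two-gland share at that visit is u/6:

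| u | two-gland share | one-gland n = 6 − u |
|---|---|---|
| 1 | 17% | 5 |
| 2 | 33% | 4 |
| 3 | 50% | 3 |
| 4 | 67% | 2 |
| 5 | 83% | 1 |
| 6 | 100% | 0 |

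The documents give neither u nor the dates, so this is a range and not an estimate.

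**3. Choice of baseline for the second injection.** Assumptions, none from the documents: n = 6; normal data; the second injection adds nothing; the gain g from the first injection persists; g is in units of the SD of a change score. With n = 6, the two-sided exact Wilcoxon signed-rank test reaches 0.05 only if all six changes have the same sign (p = 2/2⁶ = 0.031; the next possible value is 4/2⁶ = 0.0625). For change from the original baseline, the probability of p < 0.05 is therefore Φ(g)⁶ + Φ(−g)⁶. From the value just before the second injection, the true change is zero, so the probability is 2 × 0.5⁶.

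| g (SD) | original baseline | value before second injection |
|---|---|---|
| 0 | 3% | 3% |
| 0.5 | 11% | 3% |
| 1 | 35% | 3% |
| 1.5 | 66% | 3% |
| 2 | 87% | 3% |

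A simulation of 100,000 runs agrees with these rounded figures. In this illustration, a second injection with no effect looks beneficial as often as the first one's gain dictates.

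**4. What a one-gland restriction costs.** The smallest two-sided exact Wilcoxon p is 2/2ⁿ: 0.031 at n = 6, 0.0625 at n = 5, 0.125 at n = 4, 0.25 at n = 3. One acceptance leaves n = 5 at later one-gland visits, where the test cannot reach 0.05. This is a cost of the remedy and not a defect in the plan.

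**The case against.** The strongest defence has four parts.

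- **No endpoint is defined as durability of one injection.** The objective is efficacy of MSCs, and the synopsis lists both injections under the study intervention. Baseline against each visit, whatever was received, is a coherent summary of the programme as offered. This stands, and it is why the all-visits summary should be kept. It does not make that summary attributable to one or two injections, and Section 13 still describes a single unilateral injection.
- **Section 7.1 already covers much of the benefit assessment:** purpose, outcomes, timepoint and a prior assessment. This also stands. A reader might infer that the benefit of the second injection cannot be reported at all. That goes too far, since the Wilcoxon comparison could be carried over. What is missing is the baseline and the allocation of visits.
- **With no DLTs, the lower dose level was not triggered,** so evaluation by dose received can hardly mean anything except one versus two injections, apart from the 20% tolerance. That is a fair reading, but 13.3 does not state it and does not allocate visits within a re-injected subject.
- **These are exploratory analyses in six subjects.** Individual listings are planned (13.1), and a formal SAP is due before database lock (Section 13.0). This lowers the severity. It allows a later repair but states no rule, and in an open-label study the rule is better fixed before the values are examined.

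**Conclusion.** The point holds, at minor to moderate severity. Followed as written, 13.8 and 13.2 pool one-gland and two-gland values at any main visit after a second injection, and leave unused the assessment collected just before it. The amount of mixing cannot be computed. That 12 and 24 months are the most plausible visits is a judgement: the amendment was written after the 1-month objective had been met and awaited FDA review. The percentages for the choice of baseline rest entirely on the stated assumptions. The primary 1-month DLT endpoint is unaffected.

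A reader might infer three stronger points that the documents do not support.

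- **That the sub-study schedule replaces the main visits,** so that re-injected subjects lose 24-month saliva and QoL. The sub-study 24-month visit does omit them, but 7.1, 10.1 and 11.3 schedule the main visits without condition. Section 7.2 counts a subject as complete "if they have completed all visits described in the study including the last visit listed in Section 10.1: Study Calendar", and 13.1 waits for the 24-month visit.
- **That the 1-month and 3-month labels occur twice.** The sub-study visits are called 30-day and 90-day visits.
- **That the mixing can be dated.** The stagger rule in 9.7 ("A minimum interval of 14 days will occur between MSC injection of a subject and MSC injection in the subsequent subject") gives only an earliest possible date, and the stability lot in 19.4 is not identified as a subject's product.

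**What to change.** Amend 13.8 and the ANOVA sentence in 13.2, or write the following into the SAP before database lock:

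1. Summarise one-gland changes in saliva amount, composition and QoL using only visits before each subject's second injection. Give n per visit, and keep to description where n is 5 or fewer.
2. Tabulate visits after the second injection separately, by time since that injection, as change from the assessment taken just before it. State that this change is confounded with any continuing effect of the first injection.
3. Keep the all-visits summary from the original baseline, with injection status flagged at each value.
4. State in 13.3 that the evaluation by dose received separates one injection from two, and in 13.1 which 24-month visit starts the main analysis.

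The cost is wording and a few extra tables, with no new data collection. The late one-gland numbers will be small and may be zero if all six accept. Because the second injection is optional, those who remain are self-selected and may not represent the cohort.

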13.9 Interim Analyses

There is no interim analysis for this pilot study.

14.0 RISK/BENEFIT ASSESSMENT

14.1 Potential Benefits to the Subjects

The potential benefits to research subjects associated with this study include the possible improvement of radiation-induced xerostomia and hyposalivation. If this study is able to demonstrate the safety, tolerability, and possible therapeutic benefit of MSCs in radiation-induced xerostomia and hyposalivation, the community of HNC patients who undergo radiation would benefit by the availability of a treatment option. The MESRIX trial has demonstrated an improvement in salivary production and quality of life after MSC injection²⁴.

14.2 Known Potential Risks

Known Procedural Risks

- **Injection of MSCs:** The risks of MSC injection include pain or discomfort within the salivary gland; pain or discomfort at the site of injection; possible bruising and swelling around the injection site; rarely an infection, potentially diminished function of the submandibular gland, damage to small nerves that are located near the submandibular gland – this risk will be minimized by injection with ultrasound guidance.
- **Bone Marrow Aspiration:** Potential risks from bone marrow aspiration include bruising and mild transient pain around the needle site. There is a small risk of infection around the bone marrow access site that could start locally, but spread systemically. There is also a small risk of severe bleeding around the aspiration site or internally. If sedation is performed there is a small risk of slowed breathing during the procedure and nausea, headache, or feeling drowsy after the procedure.
- **Blood Draw:** The risks of drawing blood from a vein include discomfort at the site of puncture; possible bruising and swelling around the puncture site; rarely an infection; and, uncommonly, faintness from the procedure.

Known Interventional Risks

At present there has not been a defined dose limiting toxicity of MSCs and to date no serious adverse events have been reported following the infusion of either autologous or allogeneic MSCs. Of the toxicities noted so far in MSCs trials a minor (i.e. <10%) portion of patients reported a rash following infusion which can be directly linked to the cryopreservative (DMSO) used in most MSC trial where the cell dose is thawed at the bedside and immediately infused without removal of majority of

DMSO. In our trial the cells will be delivered after being thawed in media and culture rescued for 16 hours to ensure removal of DMSO and thus we do not expect to see any of these types of reactions.

Despite the strong safety profile MSC infusion has shown to date there is the slim possibility that interferon-gamma activated MSCs could result in certain systemic (acute and delayed) reactions. As such each subject will be evaluated and monitored before during and following injection of MSCs during the study.

Systemic reaction is any untoward medical hypersensitivity-like event other than injection site reaction, occurring during or after MSCs infusion administration that can be at least possibly attributed to the MSC infusion. Systemic reaction is further classified as acute and delayed based on timing and presentation of symptoms typical for hypersensitivity reactions. Acute and delayed reactions (within the first 7 days) to MSCs will be reported according to the judgment of the Investigator, based on the typical clinical features:

- Hypotension
- Urticaria
- Flushing
- Facial or hand edema
- Throat tightness
- Oral cavity or lip edema
- Headache
- Shortness of breath

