- Any hypersensitivity reaction grade 3 or higher at any time
- Any grade 3 SAE in the first 3 subjects
- Any 2 grade 3 or higher of the same SAE at any time during the study
- 5 or more grade 3 or higher SAEs that are at least possibly related at any time during the study

Dose reduction schedule:

Dose level 0 (10 x 10⁶ MSCs into one submandibular gland) given to 6 patients:

- If 0 or 1/6 patients experience DLT at dose level 0, then the dose escalation portion of a subsequent planned study will begin at dose level 0 (10 (8-12) x 10⁶ MSCs into both submandibular glands) and the study will be completed.
- If 2/6 patients experience DLT at dose level 0, then decrease dose to dose level -1 (5 x 10⁶ MSCs) and continue with unilateral injection at dose level -1.

If needed, Dose level -1 (5 x 10⁶ MSCs) given to 3 patients

- If 0/3 or 1/3 patients experience DLT at this dose level 1 then recruit additional 3 patients at this dose.
 - o If 2/3 patients experience DLT, then treatment is considered not tolerable and the study will be halted.
- If 0/6 or 1/6 patients experience DLT at this dose level, then the dose escalation portion of a subsequent planned study will begin at dose level -1 (5 (4-6) x 10⁶ MSCs into both submandibular glands).
 - o If 2/6 patients experience DLT, then treatment is considered not tolerable and the study will be halted.

Part 1 Dose-Reduction Table.

Dose Level	MSC IMP
-1	5 (4-6) x 10 ⁶ injected into one submandibular gland on Day 1
0	10 (8-12) x 10 ⁶ injected into one submandibular gland on Day 1

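### The systemic reactions named in 14.2 are not asked about item by item, and 13.7 plans no count of subjects who have one

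*Combined protocol and SAP*

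**What the plan says.** **Risk.** Protocol 14.2 states that "there is the slim possibility that interferon-gamma activated MSCs could result in certain systemic (acute and delayed) reactions". It defines the event: "Systemic reaction is any untoward medical hypersensitivity-like event other than injection site reaction", at least possibly attributable to the cells. It then lists eight features (tabulated under the working) and the reporting rule: "Acute and delayed reactions (within the first 7 days) to MSCs will be reported according to the judgment of the Investigator".

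**Collection.** The daily diary for the first month (7.1) records "occurrence and severity of other adverse events (e.g., redness, swelling, warmth, tenderness, rash, pruritis, nausea, vomiting, fatigue". Section 11.1 repeats the same nine items and leaves the list open. In 7.1 the 3-day call is for pain, and at the 1-week call the investigator is to "assess pain and ask about the area of injection regarding redness and/or swelling". The study calendar (10.1, footnote 9) and 10.3 add a general toxicity or adverse event assessment at both calls. On injection day, vital signs are taken before and 30 minutes after injection, and 14.3 gives the detection of acute systemic reactions as the reason for the 30-minute observation. Section 15.8 records all adverse events through the 1-month visit.

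**Analysis.** Section 13.7 codes all events to CTCAE v5.0, groups them by grade, attribution and expectedness, and lists them by patient. The only tabulation it gives a confidence interval is the proportion with pain below 6 (Wilson).

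**DLT and halt.** Section 9.7 counts grade 3-4 non-hematological toxicity as DLT, with exceptions. These include grade 3 rash (under 5 days in one line, down to grade 1 or less within 3 weeks in another) and "Grade 3 immune related AE (irAE) that resolves to" grade 1 or less, or to baseline, within 3 weeks on immunosuppressive treatment. Sections 9.7 and 16.5 both halt enrolment and treatment temporarily for "Any hypersensitivity reaction grade 3 or higher at any time".

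**The concern.** This is a first-in-human study of an activated cell product, and safety is its primary objective. The one risk that 14.2 ties to the activation step is systemic, but the named content of the diary and calls leans towards the injection site. A feature nobody asks about by name depends on the subject volunteering it in answer to an open question.

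At the analysis end, the headline result is the DLT proportion. A reader of the final report could see that proportion, the pain table and long listings, and still not learn how many subjects had a reaction of the kind 14.2 describes. Section 5.5 already shows the pattern: it supports the second injection with DLT, pain and serious-event results and says nothing either way about systemic reactions.

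**Working it through.** **1. The plan's own figure.** The synopsis (3.1) gives 0-64% as the 95% interval for 1 event in 6. The exact (Clopper-Pearson) lower limit is 1 - 0.975^(1/6) = 0.4%. The upper limit solves (1-p)^6 + 6p(1-p)^5 = 0.025, giving 64.1%. The figure is reproduced; the present point does not depend on it.

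**2. Features in 14.2 against the nine diary items (7.1, 11.1).** Yes means that a diary item could stand for the feature.

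| Feature | Exact wording | Rash/pruritus = urticaria, redness/warmth = flushing, swelling local only | As before, swelling anywhere |
|---|---|---|---|
| Urticaria | no | yes | yes |
| Flushing | no | yes | yes |
| Facial or hand edema | no | no | yes |
| Oral cavity or lip edema | no | no | yes |
| Throat tightness | no | no | no |
| Headache | no | no | no |
| Shortness of breath | no | no | no |
| Hypotension | no | no | no (vital signs at 30 minutes) |
| **Without a named prompt** | **8 of 8** | **6 of 8** | **4 of 8** |

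The call content stated in 7.1 (pain, redness, swelling) fills none of the gaps that remain in the last column.

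**3. Timing.** The 14.2 window is 7 days. The second call is at day 7 ± 2, so it may fall on day 5, leaving 7 - 5 = 2 days to the diary and the 1-month visit.

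**4. What incomplete detection would do (assumed values).** The documents give neither a reaction rate p nor a detection sensitivity s. With six subjects, P(at least one recorded) = 1 - (1 - p·s)^6.

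| Assumed p | s = 100% | s = 50% |
|---|---|---|
| 5% | 26.5% | 14.1% |
| 10% | 46.9% | 26.5% |
| 20% | 73.8% | 46.9% |

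For example, 1 - 0.90^6 = 46.9% and 1 - 0.95^6 = 26.5%.

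**5. Where a recorded reaction goes.**

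| Reaction | Coded and listed (13.7) | In DLT proportion | Hypersensitivity halt |
|---|---|---|---|
| Grade 1-2, non-serious | yes | no | no |
| Grade 3, non-serious, classed under a rash or irAE exception | yes | no | yes, if called hypersensitivity |
| Grade 3-4, not excepted | yes | yes | yes, if called hypersensitivity |
| Serious | yes | yes (9.7 and 13.2 add an attribution condition absent from 3.1, 6.0 and 13.7) | if grade 3 or higher and called hypersensitivity |

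No row yields a count of subjects meeting the 14.2 definition.

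**6. Precision of such a count.** With z² = 3.841, the Wilson upper limit for 0/6 is z²/(6 + z²) = 3.841/9.841 = 39.0%. For 1/6 the Wilson interval is 3.0-56.4%. The exact upper limit for 0/6 is 1 - 0.025^(1/6) = 45.9%. This width comes from n = 6, not from the gap described here.

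**The case against.** The best defence is that the plan has a general net. The diary lists are open-ended, and both calls carry a general adverse event assessment. The contralateral calls in 7.1 cover other adverse events besides pain and redness. Hypotension is checked objectively on injection day, and 15.8 records everything regardless of attribution. Rash, pruritus, nausea, vomiting and fatigue are not purely local prompts. The formal SAP, with table mock-ups, is still to be written (13.0), so a dedicated table is not excluded. All of this stands. It limits the point to missing named prompts and a missing category count.

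Three stronger readings are tempting, and the documents do not support them:

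- *Systemic reactions are never counted, or are certain to be under-detected.* Section 13.7 codes, groups and lists all events, and serious reactions and non-excepted grade 3-4 reactions enter the DLT proportion. Loss of mild events is a reasonable inference, not a documented rate.
- *The halt and the DLT rule flatly contradict each other.* A temporary halt for review and a dose-reduction count serve different purposes. The overlap requires a non-serious grade 3 reaction classed as rash or as an irAE, a term the protocol does not define.
- *Several severe reactions could accumulate among six subjects unseen.* A first grade 3 hypersensitivity reaction triggers the halt and committee and FDA review. The 14-day stagger also requires no grade 3 or higher event probably or definitely attributable to the injection. High assumed rates would sit badly with the slim possibility that 14.2 describes.

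It is also true that the first-injection phase is reported complete with no DLTs or serious events (5.5, 14.3). New prompts cannot change those data.

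**Conclusion.** The point holds as a gap in solicitation and in reporting. Four to eight of the eight features in 14.2 lack a named prompt, depending on the mapping. Throat tightness, headache and shortness of breath lack one on every reading; hypotension also does, but it is measured at 30 minutes. Mild reactions after that observation may be missed. The loss cannot be quantified from the documents: the table in step 4 rests entirely on assumed rates and sensitivities.

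Non-serious grade 1-2 reactions are outside the DLT proportion by design. A non-serious grade 3 reaction may be, if it is classed under a 9.7 exception. Neither is tallied elsewhere as a systemic reaction. Nothing here shows that a reaction occurred or that the reported DLT result is wrong. The change is worth making because it is cheap and can still apply to the contralateral injections and to the unwritten SAP.

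**What to change.** 1. Add the seven self-reportable features of 14.2 (hives, flushing, face or hand swelling, throat tightness, lip or mouth swelling, headache, shortness of breath) as prompted items in the diary and in the 3-day and 7-day call scripts. Apply this to all remaining injections, including the contralateral ones. Hypotension stays with the vital signs.
2. In the SAP, prespecify beside the DLT proportion the number of subjects with a 14.2 systemic reaction, by grade, with a Wilson 95% interval and regardless of DLT status. Show first and contralateral injections separately.
3. State in the SAP and report that first-injection data were collected without these prompts, so the two sets of counts are not directly comparable.
4. Reconcile the 9.7 rash and irAE exceptions with the hypersensitivity halt in 9.7 and 16.5, so that it is clear how one event is classified under each. Which rule should prevail is for the sponsor and the oversight bodies.

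Cost: seven diary rows, a slightly longer call script and one table. The downside is a few more trivial reports, headache being the likeliest.
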